Participants will have the option to receive secure and encrypted text messages sent via Twilio, a third party, MGB-approved web service that integrates with REDCap to send reminders, survey invitations, and collect home practice participation over SMS text messaging. If participants prefer, study staff can send “unencrypted” texts that are not secure and could result in the unauthorized use or disclosure of their information or email reminders sent directly through REDCap. If participants want to receive communication by unencrypted texts despite these risks, they will be informed that MGB Healthcare will not be held responsible for any data breaches. These texts will not contain any protected health information. Text message and data rates may apply based on participants’ cell phone service plan. Participants have the right to refuse these texting reminders. This decision will not impact their ability to participate in the study. Participants can opt out of these text messages at any time.

Outcome Measures

Primary Outcome Measures

1. Feasibility of Recruitment

We will examine feasibility of recruitment through tracking of the number who respond through flyer (QR Code), email, website or direct clinical contact.

[Time Frame: Baseline]

2. Feasibility of Assessments

We will calculate the proportion of caregivers completing the study questionnaires.

[Time Frame: Baseline, Post-intervention]

3. Feasibility of Quantitative Measures

We will assess the proportion of quantitative measures missing within the questionnaires.

[Time Frame: Baseline, Post-intervention]

Other Pre-specified Outcome Measures

4. Symptoms of Depression

We will use the Center for Epidemiological Studies-Depression Scale (CES-D). This is a 20-item scale widely used with ADRD caregivers.

[Time Frame: Baseline, Post-intervention]

5. Mindfulness

We will use the Five Facets Mindfulness Questionnaire FFMQ (15 items) to assess caregivers' mindfulness based on 5 subscales (observing, describing, awareness, non-judging, non-reactivity).

[Time Frame: Baseline, Post-intervention]

6. Perceived Stress

We will use the PSS-10 (10 items) to assess perceived stress.

[Time Frame: Baseline, Post-intervention]

7. Symptoms of Anxiety

We will use State Trait Anxiety Inventory (STAI) state subscales (20 items) to assess anxiety symptoms in response to stressful situations. STA has been successfully used with ADRD caregivers.

[Time Frame: Baseline, Post-intervention]

8. Self-Compassion

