20. Perceptions of Email and Text Reminders

We will assess caregivers' perception of emails and text messages reminders by asking, "Do you think that the amount of emails/texts you received was: too little, just enough, too much?"

[Time Frame: Post-intervention]

21. Credibility and Expectancy

We will use the Credibility and Expectancy Questionnaire (CEQ), (6 items) to assess caregivers' perceptions that the treatment will work after participating in the intervention.

[Time Frame: Pre-intervention]

The self-report measures and assessment domains align with the purpose of the study and with recommendations for feasibility trials. Feasibility of recruitment and retention will be assessed using proportions (see Table 1). Satisfaction and credibility will be assessed with proportions of scores over the midpoint of the Client Satisfaction and Credibility and Expectancy questionnaires.

4. Subject Selection

Study Population Characteristics

Conditions or Focus of Study

- Informal caregivers of people with ADRD who endorse caregiver stress and challenges managing patient behaviors

Eligibility Criteria

Caregivers will be 18 years or older, fluent in English, who meet the criteria for an informal caregiver (e.g., family or friend of a care recipient who provides unpaid care) and lives with and cares for an individual with ADRD. The informal caregivers must have lived with the patient for more than 6 months and must currently provide more than 4 hours of supervision or direct assistance to the care recipient per day (average). Caregivers will need to endorse stress (PSS-4 \geq 6) and self-report that they had managed 1 or more behavioral symptoms in the past month. Exclusion criteria include planned change in psychotropic treatment for the duration of the study, use of mindfulness apps or any meditation (more than 60 min/week in past 6 months), major illness known to drastically worsen or require surgery for the duration of the study, active treatment for cancer, involvement in another clinical trial for caregivers, a score \geq 4 on the PMSQ and no stated concerns or distress related to care recipient's disruptive behaviors.

Inclusion Criteria

- 18 years or older
- English fluency and literacy
- Meeting criteria for being a caregiver (e.g., family or friend of a care recipient who provides unpaid care)
- Must live with and care for an individual with ADRD.
- Must have been in a caregiver role for more than 6 months

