date for the next group cohort will be emailed a link with the baseline questionnaire over Redcap and offered assistance with questionnaire completion from the research assistant. Caregivers who provide consent but are unavailable to participate in the next available group will be placed on a waitlist for the next group cohort. All baselines will be completed within 1 week of the first group session. Due to the remuneration amount, participants will be prompted to complete an MGB secured REDCap survey along with the initial pre-intervention (baseline) survey that will ask for their SSN per MGH's compensation policy. If participants do not want to provide their SSN, an option will be provided to them of receiving \$50 through two gift cards (see Renumeration below). Additionally, prior to the first intervention session, caregivers will have the opportunity to attend a zoom practice session with the Research Assistant to problem-solve any technical challenges.

6. Study Procedures

Study enrollment

We will recruit up to 20 caregivers for up to 2 groups in this study. Participants will be asked to complete a baseline assessment that asks questions on physical and mental wellbeing as well as questions about their experiences as a caregiver for someone living with dementia. Upon completion, caregivers will be invited to participate in a weekly 60-minute virtual group training session for 6 weeks that is led by a trained Clinical Social Worker. The content of each session varies week-to-week: Week 1: *Understanding Caregiver Stress and Distress*; Week 2: *Mindful Caregiving*; Week 3: *Caring Without Losing Ourselves*; Week 4: *Behavior Management Skills*; Week 5: *Mindful and Self-Compassionate Caregiving*; Week 6: *Mindful and Self-Compassionate Life*. At the end of the 6 weeks, we will conduct individual live video exit interviews to gather detailed feedback on SOCIAL intervention components, applicability of study measures, general protocol issues including barriers and facilitators to participation and skill practice, perception of the web platform, and perception of the live video intervention delivery. Exit interviews will last 30 minutes and will be recorded via zoom, transcribed using Landmark Associates, and analyzed in NVivo to refine study procedures and finalize SOCIAL before the pilot RCT.

7. Risks and Discomforts

Potential risks

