It is unlikely that participants will incur any risk of physical harm because of study participation. Participants may find some questionnaire items to be emotionally upsetting or may experience psychological discomfort while discussing their experiences during intervention sessions. The study MPI [name] is a licensed psychologist and the study MPI [name] is a geriatrician. Both have expertise with ADRD caregivers and will triage and refer individual participants to an appropriate level of clinical care, as needed.

Communication-related risks: Text messages by mobile/cellphones are a common form of communication. The SOCIAL research study involves sending participants text messages using the Twilio app. Participants do not have to agree with receiving text messages in order to participate. These text messages will include information about session reminders, reminders to complete homework logs, and activity prompts to complete before upcoming sessions. We will send these messages daily during the 6-week group intervention. Texting over mobile/cell phones carries security risks because text messages between mobile/cellphones are not encrypted. This means that information you send or receive by text

message could be intercepted or viewed by someone other than staff involved with this research study, or by your mobile/cellphone provider or carrier.

Meditation-related risks. Meditation may cause study participants to feel emotions more intensely on a temporary basis (during practice) as the practice of meditation teaches participants to become more mindful of their thoughts, feelings, and emotions. Participants will learn through the instruction materials that this increase is temporary and is associated with an actual decrease in symptoms over time, due to habituation. If subjects report ongoing emotional dysregulation, the MPI, [name] will triage and refer individual participants to an appropriate level of clinical care, as needed.

8. Benefits

Potential Benefits of the Proposed Research to Human Subjects and Others

Participants may benefit from the numerous evidence-based advantages associated with engaging in meditation, self-compassion and training in managing challenging care recipient behaviors. Caregivers may experience reduced caregiving stress, emotional distress, and improved well-being. Caregivers may be able to better regulate their emotions, have fewer ruminating thoughts, and provide higher quality care to their loved ones.

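### Outcome 20 asks about emails and texts in one item, so it cannot attribute dissatisfaction to either channel for a caregiver who receives both, and no analysis by channel is planned

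*Combined protocol and SAP*

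**What the plan says.** Item 20 of the Outcome Measures in section 3 covers perceptions of both kinds of reminder. It is introduced with "We will assess caregivers' perception of emails and text messages reminders by asking", and the question is "Do you think that the amount of emails/texts you received was: too little, just enough, too much". It is asked once, post-intervention, and has three answers and no option for a channel that was not received. It is listed among the other pre-specified outcomes, not the primary ones.

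The two channels are described elsewhere:

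- **Texts are optional.** The text-messaging paragraph of section 3 states "Participants have the right to refuse these texting reminders" and "Participants can opt out of these text messages at any time".
- **Texts have a stated frequency.** Section 7, under communication-related risks, says "We will send these messages daily during the 6-week group intervention".
- **Email reminders are offered as a preference.** They appear in section 3 at the end of the sentence on unencrypted texts: "could result in the unauthorized use or disclosure of their information or email reminders sent directly through REDCap". No frequency is given.
- **Some study email goes to every enrolled caregiver.** Under section 5, those who consent and can attend "will be emailed a link with the baseline questionnaire over Redcap".

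Section 6 provides an individual 30-minute exit interview. Its topics include "general protocol issues including barriers and facilitators to participation and skill practice"; reminders are not named. Section 9 says that procedures will be revised on quantitative and qualitative data. It gives no analysis for item 20.

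**The concern.** The item is double-barrelled: it names two channels and allows one answer. A caregiver who receives both, and finds the texts too many and the emails too few, has no accurate box to tick. If that caregiver ticks *too much*, the reader cannot tell which channel is meant. Caregivers who refuse texts, or stop them part-way, answer the same question after a different exposure.

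The pilot exists to refine procedures before a randomised trial, and item 20 is the only listed outcome on reminder burden. A pooled *too much* would show that something should change without showing which channel. What is at stake is how useful one descriptive process measure will be, and no inferential claim depends on it.

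**Working it through.** The documents give no threshold, sample-size argument or analysis for item 20, so there is no stated figure to reproduce. The check is to set the reminder arrangements beside the item and ask what each pattern of exposure allows an answer to mean.

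**Inputs**

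- Enrolment: up to 20 caregivers (sections 2 and 6).
- Text frequency: daily for 6 weeks (section 7). At one text per day with no opt-out, 6 × 7 = 42 messages. One per day is an assumption.
- Email reminder frequency: not stated.
- Number receiving texts only, emails only, or both: not stated. The number receiving both can be anywhere from 0 to 20.

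**What one pooled answer tells the reader**

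| Reminders received | About texts | About emails |
|---|---|---|
| Texts only | Largely a rating of texts | Nothing |
| Emails only | Nothing | Largely a rating of emails |
| Both | Rating of the total only | Rating of the total only |
| Texts, then opted out | Rating of a shortened exposure | Depends on what replaced the texts |

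The first two rows can be recovered from the single item, provided the channel received is recorded and the answers are split by it. The plan describes no such split. The third row cannot be recovered by any split of this item.

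**Illustration, with assumed counts.** Suppose 14 of 20 caregivers receive texts, 8 of those 14 answer *too much*, and nobody else does.

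- Pooled over everyone: 8/20 = 40%.
- Among text recipients: 8/14 = 57%.

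What the 57% means depends on the emails:

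- If the 14 received texts only, 57% is a rating of texts. The gap from 40% is then a matter of reporting, and a split by channel closes it.
- If all 14 also received email reminders, 57% is a rating of the total. Of the 8 complaints, the number aimed at texts could be anything from 0 to 8, that is from 0/14 = 0% to 8/14 = 57% of text recipients. The single item cannot narrow that range.

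The counts 14 and 8 do not come from the documents. They show only where information can be recovered and where it cannot.

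**The case against.** The strongest reply is that the two-channel caregiver may not exist. Section 3 can be read as offering one preferred route per person. On that reading the item asks about whichever reminders the person had, and it is not double-barrelled for that person. The documents never say that anyone receives both reminder streams. The baseline link shows that text users get some study email, but that is not an email reminder schedule. This part of the reply stands, and it is why the affected number is given as 0 to 20.

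Three stronger readings are tempting, and the documents do not support them.

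- **A reader might infer that the pilot as a whole cannot tell which channel is the problem.** Staff must know who receives texts in order to send them, so answers could be split by channel. Refusals and opt-outs would be informative if counted. The exit interviews on general protocol issues could also surface a complaint about one channel. None of this is written down as a plan for item 20, but it is not ruled out.
- **A reader might infer that the answer cannot guide the reminder schedule of the later trial.** Total contact is a legitimate target. A clear *just enough* supports keeping the schedule, and a clear *too much* or *too little* flags a change. Nor do the documents say that this item alone will set the schedule.
- **A reader might infer that emails follow a different frequency from texts.** The email frequency is not stated, so this cannot be asserted.

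It is also fair to say that the consequence is small. Items 4 to 21 are other pre-specified outcomes (21 − 3 = 18), and this is one of them. It has no threshold and no place in the hypotheses.

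The objection does not remove the wording problem. If anyone does receive both channels, the item cannot separate them, and the plan offers no assured substitute.

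**Conclusion.** The point holds in a limited form. For any caregiver who receives both channels, item 20 cannot attribute dissatisfaction to texts or to emails, and no analysis by channel is planned even though texts are optional and sent daily. The number affected is unknown, from 0 to 20. The item keeps its value as a measure of whether total contact was acceptable, and the interviews may supply detail. This is a minor measurement point on a non-primary, descriptive outcome. It does not touch sample size, power or error rates.

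The conclusion rests on reading the item as it is worded, and on the absence of a channel-specific item or split anywhere in the document. If the investigators confirm that each caregiver has reminders by one route only, and that the route is recorded, a split by route would largely answer the point.

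**What to change.** Replace the single item with two, one on texts and one on emails. Give each the options *too little*, *just enough*, *too much* and *did not receive*. Report each among the caregivers who received that channel, and give beside it the number who refused texts at the start and the number who opted out later.

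The cost is one extra question at a single post-intervention assessment, and smaller denominators per channel. With 20 respondents one caregiver moves a proportion by 1/20 = 5 percentage points. With the 14 text recipients assumed in the illustration, one caregiver moves it by 1/14 = 7 points. For a descriptive measure used to revise procedures that is acceptable, and counts should be shown beside the percentages.

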Building on the limitations of prior research, we proposed to develop the **Supporting Our Caregivers In ADRD Learning (SOCIAL)** to help caregivers of persons with ADRD manage the stress associated with the general caregiver experience including stress stemming from managing challenging patient behaviors. In AIM 1 of the SOCIAL study (Protocol#: 2022P002037) we obtained feedback on the program's proposed content and format from caregivers of individuals living with ADRD. What we learned from those responses was used to inform this open pilot (aim 2) of the study which aims to teach: (1) mindfulness skills; (2) compassion and self-compassion skills; and (3) behavioral management skills. The SOCIAL open-pilot also provides psychoeducation and group-based training and skill practice to facilitate skill uptake and integration within the caregiver experience and tasks.

2. Specific Aims and Objectives

We will conduct a live video open pilot of the SOCIAL intervention with exit interviews (N=up to 2 groups, up to 20 caregivers). We will use this information to revise SOCIAL and our conceptual model, as needed to maximize feasibility and target engagement. Hyp. 1: SOCIAL will show evidence of feasibility, acceptability, credibility, and fidelity. Hyp. 2. SOCIAL will show evidence of improvement in intervention targets and outcomes and these improvements will be correlated.

3. General Description of Study Design

We will conduct an open pilot of our active intervention, SOCIAL, delivered via live video (Zoom) to ADRD caregivers who meet eligibility criteria. We will recruit and enroll up to 20 stressed informal caregivers of ADRD individuals who also report challenges managing patient behaviors. Participants will be adults (18 years or older) who care for an individual with ADRD and who endorse caregiver stress on the Perceived Stress Scale-4 (score of 6 or higher) and have managed 1 or more behavioral symptoms in the past month. We will recruit caregivers from an array of sources, including, but not limited to, local caregiver support programs, dementia research centers, and community partners. All recruitment efforts will be captured in a secure database and will allow us to solidify our recruitment plan for the subsequent pilot clinical trial.

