Potential participants (recruited nationally) may hear about the study through a flyer given to them from clinical staff, posted on social media or websites, or through community outreach efforts. Potential participants will either a) verbally agree to clinical staff for study staff to contact participants directly, indicate interest directly into RedCAP through the QR code or by reaching out to study staff based on information they have obtained from websites or community outreach.

Potential participants will indicate their interest by completing the REDCAP screener using the QR code on the flyer or by emailing the research assistants who will provide more information about the study and schedule a screening phone call. CRCs will reach out to eligible caregivers, and engage in an informed consent discussion where they will be informed of study procedures, expectations, potential risks and benefits of participation, and information regarding who they can contact regarding further questions. They will also be informed that participation is voluntary, that they can refuse to answer any questions, and they can withdraw from the study at any time. All caregivers who verbally consent and can attend the designated time and date for the group cohort will be emailed a link with the baseline questionnaire over REDCap; a research assistant will help with questionnaire completion if needed. All baseline data collection will be completed prior to the first group session. All caregivers will also have the opportunity to attend a Zoom practice session with the Research Assistant to problem solve any technical challenges. Caregivers will complete the same questionnaires after the conclusion of the intervention. Additionally, caregivers will have access to a web-based platform. The web platform for SOCIAL will include voice over videos and recordings of skills in addition to the program manual.

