- Must provide an average 4 hours of supervision or direct assistance per day for the care recipient
- Perceived Stress Scale-4 (4-item) version \geq 6
- Had managed 1 or more behavioral symptoms in past month

Exclusion Criteria

- Recent change in psychotropic treatment for depression or anxiety.
- Use of mindfulness apps or any meditation (more than 60 min/week in past 6 months).
- Involvement in another clinical trial for caregivers, a score \geq 4 on the Portable Mental Status Questionnaire (PMSQ).
- No stated concerns or distress related to care recipient's disruptive behaviors.
- Involvement in another clinical trial for caregivers

Recruitment and Retention Plan

We will conduct a live video (Zoom) open pilot group with exit interviews (N=up to 2 groups, up to 20 caregivers). We will use this information to revise SOCIAL and our conceptual model, as needed to maximize feasibility and target engagement.

5. Subject Enrollment

Potential participants recruited nationally will indicate their interest by completing the REDCap screener using the QR code on the flyer or by emailing the research assistants who will provide more information about the study and schedule a screening phone call. CRCs will reach out to eligible caregivers and engage in a discussion where they will be read the study fact sheet which including an explanation of study procedures, potential risks and benefits of participation, and information regarding who they can contact regarding further questions via a phone call, and if they would like to consent to participate. They will also be informed that participation is voluntary, that they can refuse to answer any questions, and they can withdraw from the study at any time. All caregivers who consent and can attend the designated time and

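### As listed, the credibility part of Hyp. 1 rests on a questionnaire given only before the first session, so it cannot show how credible caregivers find SOCIAL once they have received it

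*Combined protocol and SAP*

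**What the plan says.** Section 2 (Specific Aims and Objectives) states as Hyp. 1 that "SOCIAL will show evidence of feasibility, acceptability, credibility, and fidelity". The criterion comes at the end of the outcome list in section 3: "Satisfaction and credibility will be assessed with proportions of scores over the midpoint of the Client Satisfaction and Credibility and Expectancy questionnaires". No other measure in the list is named as a measure of credibility.

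Outcome 21 describes the six-item CEQ as a tool "to assess caregivers' perceptions that the treatment will work after participating in the intervention" and schedules it once: "Time Frame: Pre-intervention".

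Three other statements bear on timing:

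- Section 5 (Subject Enrollment) treats pre-intervention and baseline as the same occasion, in the phrase "initial pre-intervention (baseline) survey".
- Section 3 (General Description of Study Design) says "All baseline data collection will be completed prior to the first group session".
- The same part of section 3 says of the follow-up assessment: "Caregivers will complete the same questionnaires after the conclusion of the intervention".

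On what caregivers know before baseline, section 5 says that study staff "engage in a discussion where they will be read the study fact sheet which including an explanation of study procedures", together with risks, benefits and contacts.

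**The concern.** Hyp. 1 is a claim about what SOCIAL itself will show. A rating collected before anyone has attended a session can show what caregivers expect from the description they were given. It cannot show whether the rationale and skills, as the group leader presents them, are convincing.

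The pilot exists to revise the programme before a randomised pilot. If caregivers found the delivered content unconvincing, the listed credibility proportion could not register it, because every contributing score would already have been recorded. Respondents have also volunteered, consented and confirmed that they can attend a fixed slot. Favourable ratings before exposure are therefore plausible, although the documents give no figure for how favourable.

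**Working it through.** The plan states no figure for credibility, so there is nothing to reproduce. The check sets the relevant statements side by side.

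**1. What is claimed and how it is measured.** Hyp. 1 (section 2) names credibility. Section 3 measures it as the proportion of CEQ scores above the midpoint. The available text gives no required proportion.

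**2. When the CEQ is taken.** The outcome list separates its time points:

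| Outcomes (section 3) | Listed time frame |
|---|---|
| 4 to 14, the self-report targets and outcomes | Baseline and post-intervention |
| 15 (CSQ-3 satisfaction) and 16 (MPGI, perceived improvement) | Post-intervention |
| 21 (CEQ) | Pre-intervention |

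The CEQ is listed apart from both the repeated scales and the end-of-programme scales.

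**3. Where pre-intervention falls.** Section 5 equates it with baseline. Section 5 also asks for baselines within 1 week of the first session, which alone does not fix the direction. Section 3 does, by requiring all baseline data before that session.

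**4. Exposure at the time of rating.** Section 6 describes six weekly 60-minute sessions. Sessions attended before the listed CEQ: 0 of 6. Maximum data at that point: 20 caregivers × 6 items = 120 item responses, none of them following a session.

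**5. Whether another statement supplies a later CEQ.** Section 3 says that the same questionnaires are completed after the intervention. If the CEQ belongs to the baseline set, that sentence taken literally adds a second CEQ. Outcome 21 does not list one. If two CEQ scores were collected, the criterion sentence does not say which enters the proportion.

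**6. Whether the wording of outcome 21 settles it.** The description can be read as a belief, held beforehand, that the treatment will work once the caregiver has taken part. This fits the listed time frame. It can also be read as a rating made after taking part, which does not fit. The future tense favours the first reading. On that reading the wording and the time frame agree, and what is measured is expectation.

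**7. Whether another measure fills the gap.** The CSQ-3 measures satisfaction, and section 3 gives satisfaction its own proportion beside credibility. The MPGI measures perceived change in stress. The exit-interview topics in section 6 cover components, measures, barriers and facilitators, the web platform and video delivery. Credibility is not named among them, and interviews cannot supply the stated proportion.

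**The case against.** The strongest reply has four parts.

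- **A later CEQ may already be planned.** The sentence in section 3 about repeating the same questionnaires could include it. This stands as a real ambiguity, so it cannot be said flatly that no CEQ follows a session. It does not remove the point, because the specific entry for outcome 21 says otherwise and the score that enters the proportion is unstated.
- **The wording is not a contradiction.** A reader might infer that outcome 21 contradicts its own time frame. The natural reading is expected benefit, which is consistent with a pre-intervention rating. This stands, and the point does not depend on a contradiction.
- **Caregivers may know a good deal before baseline.** A reader might infer that the CEQ rates only the recruitment description. The documents do not support that. Flyers, websites, clinical staff, research assistants and the consent discussion may all convey some of the rationale. The content of the fact sheet is not in the available text, and the start of web-platform access is not given. What can be said is that the rating precedes every session.
- **Revision does not depend on the CEQ.** Exit interviews, the CSQ-3 and the MPGI all follow exposure, so an unconvincing programme could be detected by other routes. This stands and limits the harm. None of these routes tests the credibility claim in Hyp. 1.

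**Conclusion.** The point holds in a limited form. As listed, the Hyp. 1 credibility proportion comes entirely from ratings made after 0 of 6 sessions. It can describe expectation and initial credibility but not the credibility of the delivered programme. Section 3 leaves open whether a second CEQ is intended.

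A reader might go further and infer that ratings above the midpoint are assured whatever SOCIAL contains, or that a weak programme would still pass. The documents support neither. They give no expected CEQ distribution, and the available text sets no pass mark.

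The conclusion assumes that the entry for outcome 21 governs over the general sentence about repeated questionnaires, and that pre-intervention means baseline, as section 5 implies. If the general sentence governs instead, a post-exposure CEQ would exist and the remaining fault would be the conflicting schedule and the unstated choice of score.

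The impact is modest. Credibility is among the other pre-specified outcomes, no primary outcome depends on it, and the study is an open pilot of up to 20 caregivers. The change is still worth making, because it is cheap and lets the pilot answer one of its own hypotheses.

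**What to change.** 1. Reconcile outcome 21 with the section 3 sentence about repeated questionnaires, and state every occasion on which the CEQ is given.
2. Keep the pre-intervention CEQ, labelled as expectancy and initial credibility.
3. Add the six-item CEQ through REDCap after exposure. One option is after session 1 and before session 2. The other is the post-intervention battery, if section 3 is meant to include it. The first follows 1 of 6 sessions and, by session title, precedes the mindfulness (week 2) and behavior management (week 4) content. The second follows the whole programme but may lose caregivers who leave early. The plan should choose one and say so.
4. State that this post-exposure rating supplies the Hyp. 1 credibility proportion. Calculate it among those who gave a rating, and report the number not rated separately, so that attendance is not mixed with credibility.
5. Reword outcome 21 so that its description and time frame match.

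If the sponsor intends only pre-treatment expectancy, Hyp. 1 should say that instead.

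The cost is six more items per caregiver (at most 20 × 6 = 120 further item responses) and possibly a few non-responders. REDCap survey invitations and weekly home-practice collection are already planned, so no new system is needed.
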